6.1. General Considerations

Statistical analysis of this study will be the responsibility of Eli Lilly and Company (Lilly). The latest version of the Medical Dictionary for Regulatory Activities (MedDRA) will be used.

Analyses and summaries from assessment of endpoints described in the protocol are planned to be included in a clinical study report (CSR). Analyses and summaries for key safety data are also planned to be included in the CSR. Results from additional efficacy analysis and other safety analyses may also be provided in the CSR as deemed appropriate.

Any change to the data analysis methods described in the protocol will require a protocol amendment ONLY if it changes a principal feature of the protocol. Any other change to the data analysis methods described in the protocol and the justification for making the change will be described in the CSR.

All statistical processing will be performed using SAS® unless otherwise stated.

The Schedule of Visits and Procedures outlined in the protocol specifies the allowable windows for assessments. Assessments performed outside these windows will not be excluded from any analysis, unless specified otherwise.

6.1.1. Analysis Populations

Table KGAA.6.1. Analysis Populations

Population	Description
All Entered Patients	All patients who signed informed consent. The All Entered Patients population will be used for tables and/or listings of disposition that include screen failures and inclusion and exclusion criteria.
ITT Population	All patients assigned to treatment, even if the patient does not take the assigned treatment, does not receive the correct treatment, or otherwise does not follow the protocol. Patients will be analyzed according to the treatment to which they were assigned.
mITT Population	ITT population excluding all patients from Site CC and Site CC. This population will be used to summarize patient disposition, demographics, and efficacy analyses, plus to list patient data.
Safety Population	All patients who receive at least 1 confirmed dose of lebrikizumab will be included in the Safety Population.
Modified Safety Population	Safety population excluding all patients from Site CC and Site CC. Demographics, extent of exposure, treatment compliance, prior/concomitant medication use, adverse event, and immunogenicity safety analyses will be performed using the Modified Safety Population.
CCI	

Abbreviations: CC ; ITT = intent-to-treat; mITT = modified intent-to-treat.

- ^a Site CCI only participated in Studies KGAC/AD05, KGAD/AD06, KGAK/AD18, and Site CCI only participated in Study KGAK/AD18. So, analyses with only data from Studies KGAB/AD04, KGAE/AD17, and Protocol KGAA Addendum 1.1 will not be impacted.
- b The rationale for excluding patients from Site CC is in a directed site audit triggered by statistically implausible data in Study KGAD/AD06 at this study site, and the same site was also included in this Study KGAA/AD07. It was determined that some or all of the study patients at this site did not meet the eligibility criterion of having moderate-to-severe atopic dermatitis, and associated data was unreliable.
- The rationale for excluding patients from Site is a clinical site audit of lebrikizumab atopic dermatitis Studies KGAK/AD18 and KGAA/AD07 at this site which resulted in critical findings. It was determined by the audit that there was a lack of source documentation needed to substantiate eligibility for all patients enrolled at this site. Additionally, a quality issue was opened where data relating to patient's moderate-to-severe atopic dermatitis is either unreliable, inconsistent, and/or missing source documentation.

An analysis of safety in patients under 18 years of age (that is, adolescents) will be conducted as appropriate.

The number of patients included in each analysis population will be summarized.

6.1.2. Baseline Definition

The baseline used for efficacy and immunogenicity endpoints is as follows:

- The parent study baseline is used for patients with a parent study.
- The data collected at the addendum Baseline Visit 1 is used for patients who enrolled directly into Study KGAA per Protocol Addendum 1.1. If a measurement is missing at

addendum Baseline Visit 1, then the last available measurement before the first injection will be used as the patient's baseline.

The baseline used for clinical laboratory evaluations, vital signs, and other physical findings is as follows:

- For patients with a parent study, the Study KGAA baseline will be used. If Study KGAA baseline is missing, then the last available measurement from the parent study will be used.
- For patients enrolled directly per Study KGAA Protocol Addendum 1.1, the Study KGAA baseline will be used. Clinical laboratory evaluations will be processed at the Screening visit per KGAA/AD07 Addendum 1.1, and these results will be used as a laboratory evaluation analysis baseline. If the Study KGAA baseline is missing, then the last available measurement before the first injection will be used.

6.1.3. General Considerations for Analyses

Descriptive statistics will be used to summarize the efficacy and safety results. For categorical parameters, the number and percentage of patients in each category will be presented. For continuous parameters, descriptive statistics will include n (number of patients), mean, standard deviation, median, minimum and maximum.

Some summaries, such as disposition, demographics, exposure, and safety data will be performed for all data combined.

Disposition, demographics, and efficacy data will be summarized separately for the following analysis groups unless specified otherwise:

- patients coming from parent Study KGAD (DRM06-AD06) who were lebrikizumab Q2W responders in KGAD and then were randomized in Study KGAA, by treatment group in KGAA
- patients coming from parent Studies KGAD (DRM06-AD06) and KGAK (DRM06-AD18) combined
- patients coming from parent Studies KGAB (DRM06-AD04) and KGAC (DRM06-AD05) combined
- patients coming from parent Studies KGAB (DRM06-AD04) and KGAC (DRM06-AD05), received lebrikizumab 250 mg Q2W during the parent study induction period and received lebrikizumab 250 mg Q2W or lebrikizumab 250 mg Q4W during the maintenance period and are not in the escape arm.
- patients coming from parent Study KGAE (DRM06-AD17)
- patients directly enrolled per Protocol KGAA Addendum 1.1.

IGA, EASI and Pruritus Numeric Rating Scale (NRS) endpoints will also be summarized at each visit in the overall population (that is, the Study KGAA main cohort).

Other data also may be summarized using these 6 study groupings. Notably, the adverse event (AE) data will be summarized separately, for

• patients coming from parent Study KGAD (DRM06-AD06) who were lebrikizumab Q2W responders in Study KGAD and then were randomized in Study KGAA.

 patients coming from parent Studies KGAB (DRM06-AD04) and KGAC (DRM06-AD05) who received lebrikizumab 250 mg Q2W during the parent study induction period and received lebrikizumab 250 mg Q2W or lebrikizumab 250 mg Q4W during the maintenance period and are not in the escape arm.

Pruritus NRS, Sleep-loss due to Pruritus, Patient-Oriented Eczema Measure (POEM), and Skin-pain NRS are collected via eDiary. For patients directly enrolled per Study KGAA Protocol Addendum 1.1, the baseline period is the 7-day window prior to the first injection. A patient must have responses on at least 4 of 7 days to calculate a baseline weekly mean. If a patient has 3 or fewer responses, the baseline mean value will be considered missing. For other patients enrolled from a parent study, the last available weekly mean from the parent study before Study KGAA first injection will be used as Study KGAA Week 0 weekly mean. The eDiary data for Pruritus NRS, Sleep-loss due to Pruritus, POEM, and Skin-pain NRS are mapped to study visit per Appendix 1.

All safety data from this study (including Protocol KGAA Addendum 1.1) will be used as part of the integrated summaries. For the purposes of the CSR for Study KGAA (DRM06-AD07) alone, a listing and summary of serious adverse events (SAEs) and AEs leading to permanent discontinuation of the study drug will be created. For safety data from patients who enrolled from a parent study, parent study AEs that end before the first dose date of Study KGAA will not be reported to avoid double counting. For Protocol KGAA Addendum 1.1, all AEs will be reported for patients who enrolled directly into Study KGAA.

6.2. Primary and Secondary Estimands

6.2.1. Estimand of Primary Objective (Safety)

The **estimand of primary objective** is the proportion of modified Safety Population patients discontinued from study treatment due to adverse events through the last treatment visit.

6.2.2. Estimands of Secondary Objectives (Efficacy)

The secondary clinical question of interest is: what is the proportion of patients who meet the clinical requirements for response AND without discontinuation due to lack of efficacy?

The primary estimand of the secondary objective is described by the following attributes:

- A. Population: modified intent-to-treat (mITT) population as defined in Section 6.1.1;
- B. Variable: apply to all secondary endpoints.
- C. How to account for intercurrent events (ICEs):
 - a. Subjects who discontinued treatment due to lack of efficacy during Study KGAA will be considered as treatment failures, that is, nonresponders, after the ICEs. Therefore, a composite strategy will be used for these types of ICEs.
 - b. For subjects who discontinued treatment due to any other reasons, the hypothetical strategy will be used to estimate what the treatment effect would have been if subjects continued with treatment. Therefore, the hypothetical strategy will be used for these ICEs
- D. Population-level summary: response proportions or means.

The **first supportive estimand of the secondary objective** is described by the following attributes:

- A. Population: mITT population as defined in Section 6.1.1;
- B. Variable: apply to all secondary endpoints.
- C. How to account for ICEs: as observed strategy will be used, that is, only data from completers at the visit are relevant.
- D. Population-level summary: response proportions or means.

The **second supportive estimand of the secondary objective** is described by the following attributes:

- A. Population: modified ITT population as defined in Section 6.1.1;
- B. Variable: apply to all secondary endpoints.
- C. How to account for ICEs: for subjects who discontinue treatment, the hypothetical strategy will be used to estimate what the treatment effect would have been if all subjects adhered to the treatment. Therefore, the hypothetical strategy is used for these types of ICEs.
- D. Population-level summary: response proportions or means.

Analytical details on how missing data, including data missing as a result of intercurrent events, will be handled can be found in Section 6.4. Endpoints will be analyzed as described in Section 6.11 and Section 6.14. No statistical test will be performed.

Table KGAA.6.2. summarizes different analyses that will be conducted on the secondary endpoints.

Table KGAA.6.2. Analysis of Secondary Endpoints

	Treatment Discontinuation		Missing Data Imputation	
Estimand	Due to lack of efficacy	Due to any other reasons	Missing Data Imputation Method	
Primary	Composite: Set to baseline	Hypothetical: Set to missing	MCMC-MI	
Supportive	As observed	As observed	As observed analysis	
Supportive	Hypothetical: Set to missing	Hypothetical: Set to missing	LOCF	

Abbreviations: LOCF = last observation carried forward; MCMC-MI = Markov Chain Monte Carlo – Multiple imputation.

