The following efficacy assessments will be summarized at each visit they are collected:

- Change and percent change from baseline in EASI score at each visit
- Proportion of patients with EASI-50 and EASI-90 scores at each visit
- Percentage of patients with a Pruritus NRS of ≥ 4 points at baseline who achieve a ≥4 points reduction from baseline in the Pruritus NRS score at prespecified time points (for studies in which these data were collected)
- Percentage change from baseline in Pruritus NRS score at prespecified time points (for studies in which these data were collected)
- Percentage of patients with a Sleep-loss score ≥2 points at baseline who achieve a ≥2 points reduction from baseline in the Sleep-loss score at prespecified time points (for studies in which these data were collected)
- Change from baseline in sleep-loss at prespecified time points (for studies in which these data were collected)
- Percentage of patients with a Skin-pain NRS ≥ 4 points at baseline who achieve a ≥ 4 points reduction from baseline in the Skin-pain NRS at prespecified time points (for studies in which these data were collected)
- Change from baseline in Skin-pain NRS at prespecified time points (for studies in which these data were collected)
- Change from baseline in POEM scores at prespecified time points through the end of study (for studies in which these data were collected)
- Change from baseline in BSA at prespecified time points through the end of study
- Proportion of patients requiring AD concomitant treatment by visit
- Proportion of TCS/TCI free days from baseline by visit (for studies in which these data were collected).

Abbreviations: AD = atopic dermatitis; BSA = body surface area; EASI = Eczema Area and Severity Index;

IGA = Investigator Global Assessment; NRS = Numerical Rating Scale; POEM = Patient-Oriented Eczema Measure; TCI = topical calcineurin inhibitor; TCS = topical corticosteroid.

- a Achieving EASI-75 requires a ≥75% reduction in EASI scores from baseline to a later visit.
- b Pruritus NRS, Sleep-loss Score, TCS/TCI use, and Skin Pain NRS are only collected up to Week 52, not through the end of study (Week 100).

5. Study Design

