6.4. Handling of Dropouts or Missing Data

Depending on the estimand being addressed, different methods will be used to handle missing data. A description of the estimands can be found in Section 6.2.

For the primary objective, no supportive estimand or sensitivity analysis will be performed.

For the primary estimand of the secondary objective, missing data, including data missing as a result of ICEs, will be imputed based on Markov Chain Monte Carlo – Multiple imputations (MCMC-MI) as described in Section 6.4.3. An as observed analysis (see Section 6.4.1) and last observation carried forward (LOCF) (see Section 6.4.2) will be used in the supportive estimands of secondary objective.

Table KGAA.6.3 describes the planned imputation methods for efficacy and health outcome endpoints for the treatment period.

Table KGAA.6.3. Imputation Techniques for Various Variables During Treatment Period

Type of Endpoints	Efficacy and Health Outcome Endpoints	Estimand of Secondary Endpoints (Analysis Strategy for Intercurrent Events)	Missing Data Imputation Method
Categorical	IGA, EASI, Pruritus NRS, Skin Pain NRS, and Sleep-loss related categorical	Primary Estimand	MCMC-MI/As Observed ^b
	endpoints at pre-specified timepoints ^a	Supportive Estimand	As Observed, LOCF
	Remaining categorical endpoints	Supportive Estimand	As Observed, LOCF
Continuous	EASI percent change, Pruritus NRS percent change, Skin Pain NRS percent	Primary Estimand	MCMC-MI/As Observed ^b
	change, and Sleep-loss change from Baseline ^a	Supportive Estimand	As Observed, LOCF
	Remaining continuous endpoints were collected at multiple postbaseline timepoints including (but not limited to) BSA, and POEM	Supportive Estimand	As Observed, LOCF

Abbreviations: BSA = body surface area; EASI = Eczema Area and Severity Index; IGA = Investigator's Global Assessment; LOCF = last observation carried forward; MCMC-MI = Markov chain Monte Carlo multiple imputation; NRS = Numeric Rating Scale; POEM = Patient-Oriented Eczema Measure.

- ^a Pruritus NRS, Skin Pain NRS, Sleep-loss is assessed only up to week 52. Skin Pain NRS is only collected for patients enrolled from KGAK. Pruritus NRS and Sleep-loss are not collected for patients enrolled from KGAE.

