6.4.3. Markov chain Monte Carlo-Multiple Imputation

This method of imputing missing data will be used to implement the primary estimand of the secondary objective. This method will only be implemented for the following two analysis groups:

- 1. Patients coming from parent Study KGAD (DRM06-AD06) who were lebrikizumab Q2W responders in KGAD and then were randomized in KGAA, by treatment group in KGAA.
- Patients coming from parent Studies KGAB (DRM06-AD04) and KGAC (DRM06-AD05), received lebrikizumab 250 mg Q2W during the parent study induction period and received lebrikizumab 250 mg Q2W or lebrikizumab 250 mg Q4W during the maintenance period and are not in the escape arm.

For patients who discontinue from the study treatment due to lack of efficacy, set the patient's baseline value subsequent to this time through Week 100. The MCMC-MI will be used to handle the remaining missing data. Imputation will be conducted within each treatment group and for different parent studies (including Protocol KGAA Addendum 1.1) independently so the pattern of missing observations in 1 imputation group cannot influence missing value imputation in another. For each imputation process, 25 datasets with imputations will be calculated. The initial seed values are given in Table KGAA.6.4. The SAS PROC MI with MCMC option will be used to conduct the MCMC-MI. Each complete data set will be analyzed with the specified analysis. The results from these analyses will be combined into a single inference using SAS PROC MIANALYZE.

For binary responses related to EASI and IGA, the binary response variables will be calculated based on the multiply imputed datasets that have been created. As the MCMC algorithm is based on the multivariate normal model, imputed values for IGA will not generally be one of the discrete values used in IGA scoring (0, 1, 2, 3, or 4). Therefore, to derive the binary IGA response variable, standard rounding rules will be applied to the imputed values. For example, if a patient has an IGA score imputed as 1.4 (and assuming a baseline IGA score of 3), the imputed value would be rounded down to 1, and the minimum change from a baseline of 2 would have been met. This patient would be considered a responder.

For derivation of an EASI-75 and EASI-90 response, no rounding will be performed. The imputed EASI value will be compared directly to the observed Baseline EASI value to determine whether a reduction of at least 75% or 90% was achieved.

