	Proportion of patients	Descriptive analysis	mITT	All scheduled visits in the	Supplementary analysis
	achieving EASI-90	with As Observed		Treatment Period at which scales	
				are collected	
	Proportion of patients	Descriptive analysis	mITT	All scheduled visits in the	Supplementary analysis
	achieving EASI-50	with LOCF		Treatment Period at which scales	
				are collected	

Description of Efficacy/Health Outcome Analyses

			Population		
Measure	Variable	Analysis Method	(Section 6.1.1)	Time Point	Analysis Type
BSA Affected Change score	Change from baseline in BSA score	Descriptive analysis with As Observed	mITT	All scheduled visits in the Treatment Period at which scales are collected	Secondary analysis
		Descriptive analysis with LOCF	mITT	All scheduled visits in the Treatment Period at which scales are collected	Supplementary analysis
Pruritus NRS	ruritus NRS Change from baseline in Pruritus NRS	Descriptive analysis with MCMC-MI ^a	mITT	All scheduled visits in the Treatment Period at which scales are collected	Secondary analysis
Percent Change from in Pruritus NRS	Percent Change from baseline in Pruritus NRS	Descriptive analysis with As Observed	mITT	All scheduled visits in the Treatment Period at which scales are collected	Supplementary analysis
		Descriptive analysis with LOCF	mITT	All scheduled visits in the Treatment Period at which scales are collected	Supplementary analysis
	Proportion of patients achieving at least a 4-point improvement in pruritus NRS in patients who had baseline	Descriptive analysis with MCMC-MI ^a	mITT patients with baseline pruritus NRS ≥4	All scheduled visits in the Treatment Period at which scales are collected	Secondary analysis
_	pruritus NRS ≥4	Descriptive analysis with As Observed	mITT patients with baseline pruritus NRS ≥4	All scheduled visits in the Treatment Period at which scales are collected	Supplementary analysis
		Descriptive analysis with LOCF	mITT patients with baseline pruritus NRS ≥4	All scheduled visits in the Treatment Period at which scales are collected	Supplementary analysis

Description of Efficacy/Health Outcome Analyses

			Population		
Measure	Variable	Analysis Method	(Section 6.1.1)	Time Point	Analysis Type
Sleep-loss Score	Percent Change from baseline in Sleep-loss Score	Descriptive analysis with MCMC-MI ^a	mITT	All scheduled visits in the Treatment Period at which scales are collected	Secondary analysis

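### The SAP declares its primary efficacy estimand for every secondary endpoint, but BSA change and POEM change get only As Observed and LOCF, with As Observed in the lead

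*SAP*

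**What the plan says.** **Declared scope.** SAP Section 6.2.2 defines the primary estimand of the efficacy objective with the attribute "B. Variable: apply to all secondary endpoints". Its summary measure covers means as well as proportions, so continuous endpoints are in scope. The rule for lack-of-efficacy stops is: "Subjects who discontinued treatment due to lack of efficacy during Study KGAA will be considered as treatment failures, that is, nonresponders, after the ICEs". Table KGAA.6.2 repeats it without exception as "Composite: Set to baseline", gives MCMC-MI for other stops, and labels As Observed and LOCF supportive. Section 6.4.3 carries the rule out by instructing the programmer to "set the patient's baseline value subsequent to this time through Week 100".

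**Endpoints in scope.** Section 4, Table KGAA.4.1, lists among the other secondary endpoints "Change from baseline in BSA at prespecified time points through the end of study" and "Change from baseline in POEM scores at prespecified time points through the end of study". It also lists AD concomitant treatment by visit and TCS/TCI-free days.

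**What is planned.** Table KGAA.6.3 gives a primary-estimand row to IGA, EASI, Pruritus NRS, Skin Pain NRS and Sleep-loss endpoints. The row "Remaining continuous endpoints were collected at multiple postbaseline timepoints including (but not limited to) BSA, and POEM" carries the supportive estimand only, by As Observed and LOCF. In Table KGAA.6.7, "Change from baseline in BSA score" has As Observed as its secondary analysis and LOCF as supplementary, and POEM change is treated the same way. For IGA and EASI the same table makes MCMC-MI the secondary analysis and As Observed supplementary.

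**Limit by group.** Footnote b of Table KGAA.6.3, Section 6.4.3 and footnote a of Table KGAA.6.7 restrict MCMC-MI to two groups: the KGAD Q2W responders randomized in KGAA, and the KGAB/KGAC patients given Q2W in induction and Q2W or Q4W in maintenance, outside the escape arm. All other groups use As Observed.

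**The concern.** The estimand section and the method tables cannot both be followed for BSA and POEM. Under the tables, the lead result for these two endpoints describes only patients still on treatment at each visit. Section 6.4.1 itself says that such an analysis is conditional on completion and is not to be read as causal.

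The patients who leave are not a random subset. Section 5.1.2 directs that patients who do not reach or keep EASI-50 should be terminated from KGAA, so leaving because of poor skin response is part of the design. BSA and POEM measure aspects of the same disease. As such stops accumulate towards Week 100, the lead BSA and POEM means may look more favourable than the declared estimand would show, and they will not be comparable with the lead EASI results for the same group. In the randomized KGAD-responder group, which is reported by Q2W and Q4W arm, unequal lack-of-efficacy stops would enter the EASI and IGA description as failures and be left out of the lead BSA and POEM description.

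**Working it through.** The plan states no figure on this point, so there is none to reproduce. The check is a comparison of the texts, followed by an illustration.

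**Step 1. Coverage within the two MCMC-MI groups**

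| Endpoint | Secondary in Table KGAA.4.1 | Primary-estimand row in Table KGAA.6.3 | Lead analysis in Table KGAA.6.7 | Lack-of-efficacy stop in the lead analysis |
|---|---|---|---|---|
| IGA 0/1, EASI-75 | Yes (major) | Yes | MCMC-MI | Baseline value, so failure |
| EASI change, EASI-50, EASI-90 | Yes (other) | Yes, by endpoint family | MCMC-MI | Baseline value |
| BSA change | Yes (other) | No | As Observed | Absent |
| POEM change | Yes (other) | No | As Observed | Absent |
| AD concomitant treatment, TCS/TCI-free days | Yes (other) | No; not named | No row | Not stated |

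Table KGAA.6.6 says POEM is collected for patients from KGAB, KGAC, KGAD and KGAK, so both MCMC-MI groups have POEM data. BSA is a clinic-visit measure. The analysis is therefore feasible for both.

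**Step 2. Other groups.** Outside the two groups IGA and EASI are also As Observed, so BSA and POEM are handled no differently there. But no secondary endpoint then receives the primary estimand, which is a further departure from item B.

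**Step 3. Size.** Let f be the share of a group that has stopped for lack of efficacy by a visit, and m the As Observed mean change. A patient set to baseline has change 0. If the other stops, once imputed, resemble retained patients:

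- primary-estimand mean = f × 0 + (1 − f) × m = (1 − f) × m
- LOCF mean, if a stopped patient's last value keeps a share r of the retained patients' improvement = (1 − f + r × f) × m

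Both f and r are assumptions; r = 0.3 is used for illustration.

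| f | Primary estimand, % of m | LOCF at r = 0.3, % of m |
|---|---|---|
| 2% | 98.0 | 98.6 |
| 5% | 95.0 | 96.5 |
| 10% | 90.0 | 93.0 |
| 15% | 85.0 | 89.5 |

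For comparison, a binary endpoint with an assumed As Observed rate of 80% becomes 0.80 × (1 − f) = 78.4%, 76.0%, 72.0% and 68.0% at the same four values of f. That is the correction IGA and EASI receive and BSA and POEM do not.

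**Step 4. Between arms.** Suppose Q2W and Q4W have the same As Observed mean m but stop rates of 2% and 7%. As Observed shows no difference. The primary estimand shows 0.98m against 0.93m, a gap of 5% of m.

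**The case against.** The best defence is that the programmer faces no ambiguity. Section 6.2.2 sends the reader to Section 6.4 for missing data and to Section 6.11 for analyses, and both give the same methods for BSA and POEM. The stated clinical question is about a proportion of responders, so item B could be read as loose wording. This stands in part: the operational plan is consistent. But what is deferred is the analytical detail. A method table may choose how to estimate an estimand, but it does not withdraw one that has been declared. The restriction by group is stated openly in footnotes, whereas no text states or justifies a restriction by endpoint.

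Several further points stand and limit the finding:

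- A reader might infer that lack-of-efficacy stops disappear from all BSA and POEM results. They do not, because LOCF is planned for both and keeps them at their last value.
- A reader might infer that such stops always count as IGA and EASI failures. They do so only in the two MCMC-MI groups.
- A reader might call these endpoints of equal rank. IGA 0/1 and EASI-75 are major secondary endpoints; BSA and POEM rank with EASI change, EASI-50 and EASI-90.
- EASI is also reported As Observed and by LOCF, so a like-for-like comparison with BSA is available to a careful reader.
- The gap f × |m| is a difference between two estimands. It is bias only relative to the one the SAP declares primary; returning a patient to baseline is a convention.

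**Conclusion.** The contradiction is real and concerns two continuous endpoints. Section 6.2.2 item B and Table KGAA.6.2 promise a primary-estimand analysis of BSA change and POEM change that Tables KGAA.6.3 and KGAA.6.7 do not provide. The lead analysis in its place is one the SAP itself ranks as supportive.

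The size cannot be fixed from the documents. At assumed lack-of-efficacy stop rates of 2%, 5% and 10%, the primary-estimand improvement is 98%, 95% and 90% of the As Observed value, provided that other stops resemble retained patients. All analyses are descriptive, so interpretation is affected and no error rate is.

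A reader might extend the point to AD concomitant treatment and argue that lack-of-efficacy stops should count as needing treatment. The documents do not support that. Table KGAA.6.3 does not name the endpoint, Section 6.10 does not say how stops are handled, and setting to baseline has no evident meaning for it. Such a rule would redefine the endpoint. The same difficulty applies to TCS/TCI-free days. Both belong in the correction of the scope statement and not in the added analyses.

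**What to change.** 1. In Tables KGAA.6.3 and KGAA.6.7, add a primary-estimand row for BSA change and POEM change in the two MCMC-MI groups: lack-of-efficacy stops set to baseline, remaining missing values by MCMC-MI.
2. Add two seeds to Table KGAA.6.4, one for BSA and one for POEM.
3. Relabel As Observed for these two endpoints as supplementary.
4. Limit item B of Section 6.2.2 to the endpoints and analysis groups actually covered. State that AD concomitant treatment and TCS/TCI-free days fall outside it because setting to baseline is not defined for them, and that groups outside the two MCMC-MI groups are summarised As Observed for all endpoints, including IGA and EASI.
5. The revision history refers to a CSR approved on 22 January 2025. Mark the new tables as post hoc if they are produced after it.

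The cost is SAP wording, two seeds and a few more descriptive tables from existing programs. No new data are needed. The reported BSA and POEM improvements would be slightly less favourable.
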